### **II. IRB Expedited Reporting**

- a. All Investigators should also be aware of local Institutional requirements for AE reporting. For more information regarding the IRB policy, please refer to the UM HSRO's Investigator Manual: [http://hsro.med.miami.edu/documents/HRP-103\\_-\\_INVESTIGATOR\\_MANUAL\\_4.11.2014.docx](http://hsro.med.miami.edu/documents/HRP-103_-_INVESTIGATOR_MANUAL_4.11.2014.docx) and the UM HSRO SOP on New Information (HRP-024)  
<https://eprostat.med.miami.edu/eProst/Doc/0/HLJ5OTJVQEH419E0I6QPT3B199/HRP-024%20-%20SOP%20-%20New%20Information.docx>
- b. All AEs that are serious, unanticipated and (at least) possibly related will be reported to the IRB within ten (10) working days of being made known to the PI.

- c. Events that are more frequent than anticipated or more severe than expected must be reported to the IRB within ten (10) working days of being made known to the PI.
- d. All unanticipated deaths must be reported to the IRB within 24 hours of being made known to the PI.

III. Merck Expedited Reporting (Events of Clinical Interest or ECIs)

- a. In addition to the mandatory MedWatch 3500A Form, the PI is also required to comply with all reporting requirements as supplied by the Investigational Drug Sponsor: Merck.
- b. Selected non-serious and serious adverse experiences must be reported to Merck within 24 hours (and within 2 working days to Merck Global Safety) regardless of attribution to study treatment. The AEs listed and any event that meets the criteria for reporting (as noted) in the protocol **Appendix H** (event term and Grade) must be reported regardless of physician-determined causality with study medication and whether or not considered immune-related by the physician (unless otherwise specified). Physicians/study coordinators/designated site personnel are required to record these experiences as events of clinical interest (ECIs) on the Adverse Events/Experience Forms and to provide supplemental information (such as medical history, concomitant medications, investigations, etc.) about the event.
- c. Additional Sponsor Requirements:
  - i. Any other Grade 3 or higher event that the investigator/physician considers to be immune-related should be reported as an ECI regardless of whether the specific event term is in **Appendix H (Table 13)** and reported to Merck within 24 hours from the time the Investigator/physician is aware of such an occurrence. Adverse events that are both an SAE and an ECI should be reported one time as an SAE only, however the event must be appropriately identified as an ECI as well in the database (i.e. *Velos*).
  - ii. Any serious adverse event, or follow up to a serious adverse event, including death due to any cause other than progression of the cancer under study that occurs to any subject from the time the consent is signed through 90 days following cessation of treatment, or the initiation of new anti-cancer therapy, whichever is earlier, whether or not related to Merck product, must be reported within 24 hours to the Sponsor and within 2 working days to Merck Global Safety.
  - iii. Any other serious adverse event, considered by an investigator who is a qualified physician to be related to a Merck product that is brought to the attention of the investigator at any time outside of the time period specified in the previous paragraph also must be reported immediately to Merck. All subjects with serious adverse events must be followed up for outcome.
  - iv. A copy of all 15 Day Reports and Annual Progress Reports is submitted as required by FDA, European Union (EU), Pharmaceutical and Medical Devices

agency (PMDA) or other local regulators. Investigators will cross reference this submission according to local regulations to the Merck Investigational Compound Number (IND, CSA, etc.) at the time of submission. Additionally investigators will submit a copy of these reports to Merck & Co., Inc. (Attn: Worldwide Product Safety; [contact]) at the time of submission to FDA.

- v. **SAE reports and any other relevant safety information are to be forwarded to the Merck Global (ATTN: Worldwide Product) Safety [contact]**

#### IV. Pfizer Expedited Reporting Requirements

- a. For complete details always refer to the *Safety Reporting Reference Manual Investigator-Initiated Research (IIR) Studies With Pfizer Products*
- b. Complete the *Pfizer-provided Investigator-Initiated Research Serious Adverse Event (IIR SAE) Form (or other agreed reporting method as specified by and discussed with the Principal Investigator)*, and submit it to Pfizer immediately for a death or life-threatening event, and within 24 hours for all other reportable SAEs.
- c. Submit the *Pfizer-provided Reportable Events Fax Cover Sheet* with each submission of an SAE to Pfizer.
- d. Pfizer-specified “Points to Note: SAE Reporting”
  - i. IIR SAE forms (**or other agreed reporting method as specified by an discussed with the Principal Investigator**) must be submitted for all SAEs in subjects receiving a Pfizer product or blinded therapy occurring in the specified reporting period as defined in your agreement with Pfizer.
  - ii. Even those that are not study-drug-related (e.g., those associated with concomitant medications) must be reported.
  - iii. Non-serious AEs observed in the clinical trial are NOT submitted.
  - iv. Specifically excluded from the reporting requirements for SAEs under this provision is any SAE identified in the protocol as anticipated to occur in the study population at some frequency independent of drug exposure, unless the Principal Investigator assesses such an event as related to the Pfizer Product.

v.

**APPENDIX B: DATA SUBMISSION SCHEDULE**

CASE REPORT FORM(S)	TIMEPOINT TO BE COMPLETED
Pre-Treatment	
ICF, including HIPAA signed/dated	Prior to registration
Eligibility Checklist	
SCCC Protocol Enrollment Form	
On-study Form	e.g. Within 30 days of registration
On Treatment	
Treatment Form Cycle X, Day Y	e.g. Due every cycle for phase II studies
End of Treatment	
Off Treatment Form	Within 14 days of discontinuation/completion of protocol therapy
Follow-Up (for studies with long term follow-up)	
Follow-up Form	Every 3 months if < 2 years from study entry; Every 6 months is 2-5 years from study entry; Every 12 months if more than 5 years from study entry
Progression/Relapse	Within 4 weeks of knowledge of progression/relapse
Notice of Death Form	Within 4 weeks of knowledge of death
Subsequent Malignancy	Within 4 weeks of knowledge of another malignancy

**APPENDIX C: PERFORMANCE STATUS SCALES**

PERFORMANCE STATUS CRITERIA					
ECOG (Zubrod)		Karnofsky		Lansky	
Score	Description	Score	Description	Score	Description
0	Fully active, able to carry on all pre-disease performance without restriction.	100	Normal, no complaints, no evidence of disease.	100	Fully active, normal.
		90	Able to carry on normal activity, minor signs or symptoms of disease.	90	Minor restrictions in physically strenuous activity.
1	Restricted in physically strenuous activity but ambulatory and able to carry out work of a light or sedentary nature, e.g., light housework, office work.	80	Normal activity with effort, some signs or symptoms of disease.	80	Active, but tires more quickly.
		70	Cares for self, unable to carry on normal activity or do active work.	70	Both greater restriction of, and less time spent in, play activity.
2	Ambulatory and capable of all selfcare but unable to carry out any work activities. Up and about more than 50% of waking hours.	60	Requires occasional assistance, but is able to care for most of his/her needs.	60	Up and around, but minimal active play; keeps busy with quieter activities.
		50	Requires considerable assistance and frequent medical care.	50	Gets dressed, but lies around much of the day; no active play; able to participate in all quiet play and activities.
3	Capable of only limited selfcare, confined to bed or chair more than 50% of waking hours.	40	Disabled, requires special care and assistance.	40	Mostly in bed, participates in quiet activities.
		30	Severely disabled, hospitalization indicated. Death not imminent.	30	In bed, needs assistance even for quiet play.
4	Completely disabled. Cannot carry on any selfcare. Totally confined to a bed or chair.	20	Very sick, hospitalization indicated. Death not imminent.	20	Often sleeping, play entirely limited to very passive activities.
		10	Moribund, fatal processes progressing rapidly.	10	No play, does not get out of bed.
5	Dead	0	Dead	0	Dead

**As published in Am J Clin Oncol:** Oken MM, Creech RH, Tormey DC, Horton J, Davis TE, McFadden ET, Carbone PP. Toxicity and Response Criteria of the Eastern Cooperative Oncology Group. Am J Clin Oncol 1982;5:649-655. The Eastern Cooperative Oncology Group, [name], Group Chair.

## APPENDIX D: NYHA CLASSIFICATION OF HEART DISEASE

New York Heart Association (NYHA) classification of heart disease

NYHA Class	Symptoms
I	No symptoms and no limitation in ordinary physical activity, e.g. shortness of breath when walking, climbing stairs etc.
II	Mild symptoms (mild shortness of breath and/or angina) and slight limitation during ordinary activity.
III	Marked limitation in activity due to symptoms, even during less-than-ordinary activity, e.g. walking short distances (20–100 m). Comfortable only at rest.
IV	Severe limitations. Experiences symptoms even while at rest . Mostly bedbound patients.

## APPENDIX F: BIOMARKER, CORRELATIVE AND SPECIAL STUDIES

[figure not shown]
### **A. Exploratory Objective 1: Characterization of immunomodulatory factors in patients treated with concurrent axitinib/pembrolizumab**

#### Rationale and Preliminary Studies:

Although the immune system is suspected to play a role in sarcoma development and recurrence, the specific mediators of immune surveillance and suppression of tumor growth are largely unknown. Additionally, we have learned from analysis of patients treated thus far with PD-1-directed therapy that biomarkers of response to immunotherapy are extremely complex. Although PD-L1 expression in tumor cells and the presence of lymphocyte infiltration with PD-1/PD-L1 expression seem to be the best predictors of response, 10-15% of patients without tumor PD-L1 expression have responded to therapy, suggesting that other immunomodulatory factors must be playing a role. In addition to CTLA4 expression, other negative regulatory receptors have also been implicated, including LAG-3 and TIM-3, with pre-clinical blockade of some of these pathways resulting in improved anti-tumor response. Finally, the presence of myeloid-derived suppressor cells (MDSCs) and regulatory T-cells have been shown to negatively impact response to therapy in many cancers, though these are also understudied in sarcomas.

Thus, a key correlative component of our study will be to profile sarcoma tumors and infiltrating tumor lymphocytes using pre- and post-treatment tumor biopsies, and analysis of circulating peripheral blood mononuclear cells to better understand the immune environment in sarcoma patients. **We aim to define changes in intra-tumoral and peripheral blood lymphocyte phenotypes, activation and differentiation markers, and checkpoint ligand expression after treatment with axitinib/pembrolizumab, and correlate with radiographic response to therapy.**

As discussed in Section 2.6, our preliminary studies demonstrated PD-L1 expression in 9 of 10 sarcoma patients, TIL infiltration in all patients, and evidence of increased TIL infiltration and PD-L1 expression in tumors refractory to prior therapy. Using dispase/collagenase digestion as detailed below, a single cell suspension was prepared from freshly harvested sarcoma tissue from a patient undergoing surgery. One million dissociated tumor cells were stained with live/dead dye, CD3, CD4, CD8, CD45, and CD27 and analyzed using FACS. From  $1 \times 10^6$  dissociated tumor cells, 15,000 CD3+ lymphocytes were detected, including 10,600 CD4+ and 4200 CD8+ (Figure F1). Most of the cells in the tumor were central memory (Tcm) or functional effector memory (Tem) phenotypes, with largely depleted naïve fractions. This demonstrated feasibility of isolating a sufficient number of lymphocytes from fresh sarcoma tissue for analysis using this technique.

**Figure F1. TIL phenotype determined by flow cytometry.** After excluding doublets by height/width gating, the live cells were gated by live/dead dye exclusion. From  $1 \times 10^6$  dissociated tumor cells, we were able to detect 15,000 CD3+ cells. Of those 10,600 were CD4+ and 4,200 were CD8+ cells. We were able to determine the memory phenotype and found most of the cells in the tumor were Tcm (CD45RA-/CD27+) or Tem (CD45RA-/CD27-) cells. In particular, the CD4 compartment were largely depleted of their naïve fraction (CD45RA+CD27+). (Courtesy of [name]/[name], University of Miami, unpublished data.)

Approach:

1. Analysis of tumor biopsies by immunohistochemistry ([name], Department of Pathology
  - a. A single core biopsy specimen will be collected in formalin and transported to [name] in the Department of Pathology (detailed in Section 14). Due to the inefficiencies in traditional immunohistochemistry which require a large number of slides, we have opted to partner with [name] at MD Anderson Cancer Center who have been performing multiplex IHC on multiple sarcoma trials utilizing immunotherapy. IHC will be performed on FFPE samples using validated antibodies and standard immunohistochemistry procedures for the following markers:

Panel 1	Panel 2	Panel 3
PD-L1	CD3	LAG-3
CD68	CD8	TIM-3
PD-1	Granzyme B	ICOS
CD8	CD45RO	OX-40
CD3	FOXP3	CD3
AE1/AE3	AE1/AE3	AE1/AE3
Co-localizations Report:	Co-localizations Report:	

 
Percentage of Malignant cells PD-L1+ (AE1/AE3+PD-L1+)
 
Total T-cell lymphocytes (CD3+)
 
T-cells antigen-experienced (CD3+PD-1+)
 
Cytotoxic T-cells (CD3+CD8+)
 
Cytotoxic T-cells antigen-experienced (CD3+CD8+PD-1+)
 
Total macrophages (CD68+)
 
Macrophages PD-L1+ (CD68+PD-L1+)
 
	
 
Total T-cell lymphocytes (CD3+)
 
Cytotoxic T cells activated (CD3+CD8+Granzyme B+)
 
Effector/memory cytotoxic T cells (CD3+CD8+CD45RO+)
 
Regulatory T cells [(CD3+FOXP3+)-(CD3+CD8+FOXP3+)]
 
	

Figure F2 –

Multiplex immunohistochemistry panels to be performed on tumor biopsies in collaboration with [name] at MD Anderson.

- b. The immune cell infiltrate in the tumor will be assessed according to the intensity and geographic distribution within the tumor. The percentage of the immune infiltrate subset (leukocytes - CD45+, T-lymphocytes - CD3+, macrophages - CD68+) is calculated by dividing the total number of each cell type by the total number of cells present in each 20X microscopic power field. A semiquantitative scoring system for the distribution of the cells is 0-3; 0 = no infiltrate; 1 = focal infiltrate, <5%, mostly perivascular in the tumor with some intratumoral extension; 2 = moderate infiltrate, 5-50%, prominent intratumoral and intermingling with neoplastic cells; 3 = extensive infiltrate, >50%, obscuring tumor cells.
- c. PD-L1 expression (cytoplasmic and cell membrane) by tumor cells and tumor infiltrating immune cells are independently scored by devising a percentage which is calculated by dividing the number of PD-L1 positive specific cells by the total number of each respective cell type. The positivity is scored as negative (0%), low (<5%), intermediate (5-50%) and high (>50%).

- d. PD-1 expression (cytoplasmic and cell membrane) is evaluated in CD3+ T cells using percentage calculated by dividing PD1 positive cells by total number of CD3+ T cells. The positivity is scored as negative (0%), low (<5%), intermediate (5-50%) and high (>50%).
  - e. Statistical analysis and outcomes are detailed in section 16.3.
2. Analysis of tumor biopsies for immunomodulatory markers (Flow cytometry)
- a. 2-4 needle core biopsy specimens will be collected in RPMI media and immediately transferred to [name] laboratory.
  - b. A single cell suspension will be made from the biopsies by digesting tissue with dispase/collagenase (Roche Liberase DH) in media with addition of DNase at 37 degrees, and single cells isolated using a Ficoll gradient.
  - c. Cells will be stained with antibodies as per Table F1, followed by FACS analysis to profile tumor infiltrating lymphocytes. This panel allows for the determination of memory/naïve T cell markers, Treg, and markers associated with negative regulation of T cells.
  - d. Statistical analysis and outcomes as per Section 16.3.

Target	Clone	Fluorochrome	Purpose
CD3	UCHT1	BV570	T cells
CD4	RPA-T4	BV650	T helper subset
CD8	RPA-T8	PerCP-Cy5.5	T cytotoxic subset
CD25	M-A251	PE-Cy7	Treg/Activation
CD27	M-T271	APC-H7	Naïve/Memory
CD45RA	HL100	BV711	Naïve/Memory
CD127	HIL-7R-M21	BB-515	Treg gating
CD152 (CTLA4)	BNI3	BV421	Checkpoint
CD223 (Lag-3)	3DS223H	PE	Checkpoint
CD279 (PD-1)	EH12.1	BV786	Checkpoint
Tim-3	F38-2E2	APC	Checkpoint

Live/Dead	Invitrogen kit	Aqua	Gate on live cells
Dump CD14/16/19/56	Various	PE-CF594	Exclude non-T cells

**Table F1. Antibody panel for flow cytometry evaluation of tumor-infiltrating lymphocytes.**

3. Analysis of circulating peripheral blood mononuclear cells for immunomodulatory markers and activation (Flow cytometry)
  - i. Peripheral blood samples will be collected by phlebotomy
    - a. 60 cc blood heparinized (green top tubes) and 10 cc EDTA-anticoagulated (purple top tubes) for plasma and immediately transferred to [name] laboratory.
  - ii. Blood samples will be processed by Ficoll gradient to isolate serum, peripheral blood mononuclear cells, and plasma.
  - iii. PBMC will be stained with antibodies as per Table F2. Due to the higher numbers of cells, we will repeat the same antibodies used in the TIL panel, but with additional markers to identify T-regulatory cells and more thoroughly assess activation status.
  - iv. Residual PBMC pellets and serum will be cryopreserved for future potential studies.
  - v. Statistical analysis and outcomes as per section 16.3.

Target	Clone	Fluorochrome	Purpose
CD3	UCHT1	BV570	T cells
CD4	RPA-T4	BV650	T helper subset
CD8	RPA-T8	PerCP-Cy5.5	T cytotoxic subset
CD25	M-A251	PE-Cy7	Treg/activation
CD27	M-T271	APC-H7	Naïve/Memory
CD45RA	HL100	BV711	Naïve/Memory
CD152 (CTLA4)	BNI3	BV421	Checkpoint
CD223 (Lag-3)	3DS223H	PE	Checkpoint
CD279 (PD-1)	EH12.1	BV786	Checkpoint

Fox-P3	259D/C7	Alexa 647	Treg
Ki-67	B56	Alexa 488	Proliferation
Live/Dead	Invitrogen kit	Aqua	Gate on live cells
Dump CD14/16/19/56	Various	PE-CF594	Exclude non-T cells

**Table F2. Antibody panel for flow cytometry evaluation of circulating lymphocytes.**

**4. Analysis of tumor biopsies and circulating lymphocytes for RNA expression analysis of key angiogenic and immune-related genes**

In collaboration with Nanostring, we will utilize a novel, 770-gene Universal Immunooncology panel to analyze pre-treatment tumor biopsies to identify immune signatures that correlate with PFR at 3 months. Additionally, we will compare immune signatures of the on-treatment biopsies to baseline which may reveal additional biomarkers of response, but also clarify mechanism of activity by including analysis of angiogenesis genes. In parallel, we will partner with Simpatica Medicine to perform similar analysis on RNA expression data from sequenced PBMC samples pre- and post-treatment.

**5. Analysis of functional VEGF activity from peripheral blood**

In collaboration with [name], we will quantify circulating endothelial cells (CEC) and endothelial progenitor cells (CPC), and determine plasma angiogenic activity as previously described. In the ASPS expansion patients, we will also collect PBMC/plasma at Cycle 1 Day 8 prior to pembrolizumab to assess effects from axitinib alone. We will use flow cytometry to measure the concentrations of CEC and CPC in mononuclear cells. Angiogenic activity of patient plasma samples at baseline and after treatment with axitinib or axitinib/pembrolizumab will be measured by exposing plasma samples to human umbilical vein endothelial cells in vitro (HUVEC cell line, Lonza). The resulting proliferation of endothelial cells will be measured using a colorimetric assay. Changes in angiogenic activity will be correlated with patient responses and the maximum dose of axitinib achieved for each patient.

**6. Identify clonal populations and the associated tumor-specific antigens of tumor-infiltrating and circulating T cells in alveolar soft part sarcoma patients with clinical responses to axitinib/pembrolizumab therapy**

After collecting TIL and PBMC from the expansion ASPS cohort as previously described, we will extract RNA using a microRNAeasy kit (Qiagen). In collaboration with our Oncogenomics core facility, quality and quantity of RNA will be assayed followed by library prep to identify T cell receptors corresponding to unique clones (PCR using the ArcherDX Immunoverse kit). The

libraries will be quantified and sequenced on the Illumina NextSeq sequencer, and analyzed using the ArcherDX immune repertoire analysis software platform. Once we have quantified T cell clones, we will compare baseline to on-treatment frequencies, as well as clonality of TIL vs. peripheral T cells for each patient. We will also compare frequencies of T cell clones across ASPS patients. We will perform confirmatory FISH for the ASPS1-TFE3 fusion as well as whole exome sequencing on baseline tumor samples and utilize existing databases to generate a list of candidate epitopes. In all steps, we will collaborate with Bioinformatics and Oncogenomics core facilities at SCCC.

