- Plasma angiogenic activity at baseline and the ratio between on-treatment (either Cycle 1 Day 8 or Cycle 3 Day 1) and baseline.

Evaluable criteria: Eligible patients who receive at least one cycle of study drug and undergo at least one post-treated radiographic imaging study.

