**Table 5. Summary of Non-Lab DLTs.**

### 8.0 TREATMENT PLAN

A cycle of treatment will consist of concurrent axitinib and pembrolizumab therapy for 6 weeks (Figure 3, Table 6), except for cycle 1 which will be 7 weeks as detailed above. Administration of axitinib shall occur continuously with pembrolizumab administered on day 8 and day 29 of the first cycle, and days 1 and 22 of the following cycles. The first five patients will not be dose-escalated above 5 mg PO twice daily axitinib. If these patients exhibit acceptable rates of DLT, starting with patient 6, dose-escalation of axitinib will be permitted. No dose escalations will be permitted during cycle 1. On day 1 of cycle 2 and the subsequent cycles, dose escalation of axitinib is permitted if toxicity is within the specified criteria. No dose-escalation will be conducted in the middle of any cycle. Dose reduction or interruption is permitted in the case of toxicity at any time as per section 10.0.

Trial treatment should be administered after all procedures/assessments have been completed as detailed in Section 12.0. Trial treatment may be administered up to 3 days before or after the scheduled Day 1 of each cycle due to administrative (e.g. scheduling) reasons.

Cycle(s)	1							2						Imaging prior to every subsequent odd cycle (i.e. 3, 5, 7, 9, etc.)	3, 4, 5, etc. until progression					
	1	2	3	4	5	6	7	1	2	3	4	5	6		1	2	3	4	5	6
Week(s)	1	8	1	2	2	3	4	1	8	1	2	2	36	1	8	1	2	2	3	
Day(s)	1	8	5	2	9	6	3	1	8	5	2	9	36	1	8	5	2	9	6	
Axitinib oral, BID continuously (uptitration permitted starting from cycle 2)	X	X	X	X	X	X	X	X	X	X	X	X	X	X	X	X	X	X	X	
Pembrolizumab IV q21 days		X			X			X			X			X			X			

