## 10.2 Dose Titration Guidelines for Axitinib

All patients will begin therapy at the starting dose level of 5 mg PO twice daily. Patients will be evaluated closely during cycle 1 for adverse events, laboratory studies, and review of study diaries and blood pressure logs. Additionally, patients will be instructed to call with any adverse events between study visits. **If there is no grade 2 or greater toxicity on cycle 2 day 1, the patient will be eligible for dose escalation of axitinib as per Table 8. Dose escalation DURING a cycle is not permitted. Consideration of escalation should only be done on day 1 of all subsequent cycles. If a patient is dose-escalated on day 1, they should resume blood pressure monitoring daily during the first three weeks of that cycle until evaluated during week 4 (i.e. day 22) visit of that same cycle.**

Dose reductions for grade 2 or greater toxicities may be done at any time during the cycles as per the following guidelines, and Tables 8 and 9.

- For grade 2 or greater fatigue, hand-foot syndrome, mucositis, or diarrhea, attempt medical supportive care first: (topical creams, anti-diarrheal, magic mouthwash or similar).
- If no improvement within 3 days, dose reduce axitinib as per Table 8.
- Axitinib may be held for 3-5 days prior to dose reduction in the judgment of the treating investigator, particularly for grade 3 toxicities

Management of Axitinib-related Hypertension:

- Patients will be provided with blood pressure cuffs and monitoring sheets. They will be instructed to monitor their blood pressure once daily before the evening dose of axitinib. They are to notify the study team for BP  $\geq$  150/100 mm Hg or for BP  $\geq$  120/80 mm Hg with any symptoms perceived to be related to BP (headache, chest pressure, shortness of breath, dizziness, blurry vision).
- Medications are to be added and titrated aggressively. Preferred sequence as follows:
  - Calcium channel blockers: (amlodipine, nifedipine, diltiazem, etc.)
  - ACE inhibitors or ARB (lisinopril, valsartan, losartan, etc.)
  - Diuretics (hydrochlorothiazide, furosemide). Patient should be prescribed concurrent potassium and magnesium supplementation and scheduled for potassium and magnesium laboratory tests within three days of starting.
  - Avoid beta-blockers, clonidine, digoxin.
  - If BP still  $\geq$  150/100 mm Hg despite maximal doses of three anti-hypertensive medications, axitinib should be reduced by one dose level.

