### 13.2 On Treatment Specimen Collection

#### 13.2.1 Cycle 3, Day 1 (PRE-DOSE)

For patients who have successfully completed two cycles of axitinib/pembrolizumab therapy, the following on-treatment correlative studies will also be performed:

- 5 core biopsies (minimum of 2), 18-22 gauge in diameter and at least 1 cm in length, will be obtained. The interventional approach used to obtain the sample (ultrasound or CT guided biopsy) will be selected by the medical personnel performing the biopsy. If possible, the biopsy site should be in the same tumor initially biopsied prior to therapy.
  - One needle core biopsy will be transported in formalin to pathology for immunohistochemistry evaluation of immunologic markers. This analysis will be performed in collaboration with [name] at MD Anderson Cancer Center. Samples will be deidentified and sent to his laboratory for multiplex immunohistochemistry.
  - Unstained slides from the formalin fixed biopsies will be sent to Nanostring for RNA expression analysis using the Universal Immunooncology Expression Panel under a collaborative research agreement to identify potential biomarkers of response.
  - The remaining cores (if any) will be collected in cell culture media and transported to the [name] lab for preparation of a single cell suspension, isolation of lymphocytes, and immediate analysis by flow cytometry. For expansion patients, additional cores will be collected for RNA analysis and performance of T cell receptor sequencing and clonality assays using the Archer DX platform.
- Patients will also undergo phlebotomy for analysis of circulating mononuclear cells with banking of serum fractions for later analysis.
  - (6) 10 cc green top tubes and (1) 10 cc purple top tube will be collected for each time point. Samples will be separated using a Ficoll gradient. Mononuclear cells will be removed, washed, treated with RBC lysis process, then either stained immediately for flow cytometric analysis or frozen for later use. Aliquots of plasma will also be frozen. One tube of PBMCs will be preserved in RNA later for T cell clonality assays using the ArcherDX platform.
  - Banked PBMCs will be sent out to Simpatica Medicine for RNA expression analysis to identify potential biomarkers of response under a collaborative research agreement.

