immune-related response criteria. PET/CT will be obtained at baseline, Cycle 3, and off-study and tumor response analyzed by PERCIST 1.0.

- The quantity of circulating tumor cells (CTCs) in peripheral blood will be measured at three timepoints: baseline, cycle 3, and off-study.
- RNA expression of a panel of angiogenesis and immune related genes performed using Nanostring Universal Immunooncology platform on tumor biopsies. RNA expression of immune related genes will be performed on banked peripheral blood samples by Simpatica Medicine. Expression profiles will be obtained at baseline and at Cycle 3 Day 1 on treatment.

T cell clonality indices of tumor biopsies and peripheral blood at baseline and on treatment at Cycle 3 Day 1.

Plasma angiogenic activity at baseline, Cycle 1 Day 8, and Cycle 3 Day 1.

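### Maximum axitinib dose is not aligned in time with the angiogenic samples it is correlated with, so the correlation mixes exposure, tolerance and time on treatment

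*Combined protocol and SAP*

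**What the plan says.** Appendix F, A.5 gives the analysis in one sentence: "Changes in angiogenic activity will be correlated with patient responses and the maximum dose of axitinib achieved for each patient". It names no coefficient, no time window for the maximum and no adjustment.

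Section 3.3 defines the endpoint as "Plasma angiogenic activity at baseline and the ratio between on-treatment (either Cycle 1 Day 8 or Cycle 3 Day 1) and baseline". Section 16.2 lists "Plasma angiogenic activity at baseline, Cycle 1 Day 8, and Cycle 3 Day 1". The Day 8 sample belongs to the expansion cohort: "In the ASPS expansion patients, we will also collect PBMC/plasma at Cycle 1 Day 8 prior to pembrolizumab to assess effects from axitinib alone". The Cycle 3 Day 1 blood is drawn before dosing, from patients who have completed two cycles (Section 13.2.1).

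On dosing, everyone starts at 5 mg twice daily (Section 10.2). Section 8.0 states: "No dose escalations will be permitted during cycle 1". Section 10.2 adds: "Consideration of escalation should only be done on day 1 of all subsequent cycles". Table 10 moves one level at a time through 5, 6, 7, 8 and 10 mg, subject to the absence of specified grade 2 or greater toxicity. The five safety lead-in patients are not escalated above 5 mg (Section 8.0).

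Section 16.3 contains no analysis of angiogenic activity against dose, so the Appendix F sentence is the only specification.

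**The concern.** A dose reached after a blood sample cannot have influenced that sample. If most of the range of maximum dose arises after the angiogenic change has been measured, the correlation is not a dose-response estimate. Two consequences follow.

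- Later escalation adds variation unrelated to exposure at the sample, which weakens any true dose effect.
- Higher levels need both good tolerance and continued treatment. If angiogenic change is itself prognostic, patients with a favourable change stay on longer, have more chances to escalate and show a higher maximum. An association with dose can then appear without any dose effect.

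The maximum also ignores reductions. A patient escalated to 6 mg and then reduced keeps a maximum of 6 mg, although the sample reflects a lower dose.

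What is at stake is the reading of one exploratory correlative result. No primary or secondary analysis, stopping rule or dosing rule depends on it.

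**Working it through.** The plan gives no power or effect size for this correlation, so there is no figure of its own to reproduce. The 89.4% power in Section 16.4 does reproduce (two-sample t-test, 10 and 20 patients, difference 2.5, SD of change √(2 × (1 − 0.2)) = 1.265, two-sided level 0.05/60). It compares responders with non-responders and does not concern dose.

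**Step 1: calendar.** Cycle 1 lasts 49 days and later cycles 42 days (Sections 7.0 and 8.0). Cycle 2 Day 1 is day 49 + 1 = 50, and each later cycle adds 42. The dates are nominal; Section 8.0 allows 3 days either way.

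| Earliest day | Visit | Highest dose from then |
|---|---|---|
| 1 | Cycle 1 Day 1 | 5 mg |
| 50 | Cycle 2 Day 1 | 6 mg |
| 92 | Cycle 3 Day 1, after the sample | 7 mg |
| 134 | Cycle 4 Day 1 | 8 mg |
| 176 | Cycle 5 Day 1 | 10 mg |

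At Cycle 1 Day 8 the ceiling is 5 mg; at Cycle 3 Day 1 before dosing it is 6 mg. All four steps follow the first sample and three of four follow the second. The highest possible mean dose over the 91 days before the second sample is (49 × 5 + 42 × 6)/91 = 5.46 mg twice daily, on a maximum-dose scale that runs to 10 mg.

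**Step 2: who can reach the later levels.** Assume exponential time on treatment governed by PFS, so the share still on treatment after t days is p^(t/91.3), where p is the 3-month PFS rate. At the design value of 40% (Section 16.4), 0.40^(91/91.3) = 40% reach Cycle 3 Day 1 and 0.40^(175/91.3) = 17% reach Cycle 5 Day 1. At an assumed 60%, the shares are 60% and 38%.

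**Step 3: simulation.** There were 4,000 runs per setting, using Spearman correlation. N = 40 and the 40% rate come from the plan. The assumptions are other PFS rates (up to 60% at Cycle 3 Day 1, up to 80% at Cycle 1 Day 8), a per-cycle chance of escalation of 0.4, 0.7 or 0.9 that ends at the first failure, and a biomarker-prognosis correlation of 0 or 0.5. Dose reductions, the lead-in cap and treatment beyond progression were not modelled.

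Cycle 3 Day 1, N = 40 enrolled:
- Between 16% and 81% of sampled patients end with a maximum above their dose at sampling.
- No dose effect, biomarker-prognosis correlation 0.5: mean correlation with maximum dose is 0.00 to 0.13, with rejection in 5% to 10% of runs at a nominal 5%. With dose at sampling the mean is about 0.00.
- True effect of 0.5 SD per mg, no prognostic link: mean correlation is 0.07 to 0.22 with maximum dose and 0.14 to 0.23 with dose at sampling.

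Cycle 1 Day 8, N = 10, no dose effect:
- Biomarker-prognosis correlation 0.5: mean correlation with maximum dose is 0.08 to 0.37, with rejection in 5% to 20% of runs.

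With neither a dose effect nor a prognostic link, the mean correlation is about 0 at both times.

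**The case against.** A reader might infer that the correlation reflects survival on study and not exposure, or that it cannot show a dose effect at all. The documents do not support that.

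- Maximum dose also depends on tolerance (Section 10.2, Table 10) and on the lead-in cap, which holds five patients at 5 mg however long they stay.
- Everyone sampled at Cycle 3 Day 1 has completed two cycles, and 5 versus 6 mg during cycle 2 is real exposure before that sample. The simulations show dilution, not absence.
- Progression does not strictly end escalation. Section 11.0 lets some patients continue after RECIST progression, and Section 10.2 does not bar escalation for them.
- The spurious association needs a prognostic biomarker and is small at Cycle 3 Day 1. Immortal-time bias is a loose label, since no survival time is compared between dose groups.
- That the result would be taken to support titration is conjecture; Section 1.4 rests on renal cell carcinoma data.

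Two further points are fair. Plasma is also assayed at end of treatment (Section 13.3), after the maximum has been reached. That does not rescue the analysis. The sample is outside the endpoint in Sections 3.3 and 16.2, and Section 13.3 times it 30 days after the last dose. With a half-life of at most 6.1 hours (Section 9.1.3), that is 720/6.1, or about 118 half-lives off drug. Also, the choice of "the ratio between on-treatment (either Cycle 1 Day 8 or Cycle 3 Day 1) and baseline" need not mean pooling: Section 16.2 lists the times separately and A.5 distinguishes axitinib alone from the combination. A clarifying sentence is enough there.

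Finally, the dose correlation is not a listed objective, and Section 16.3 calls the correlative analyses exploratory. This limits the weight of the point but does not remove the mismatch.

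**Conclusion.** The point holds as a matter of timing, and it is minor. The mismatch follows from the plan's own schedule and needs no assumption beyond nominal visit dates. For the listed endpoint samples, maximum dose is largely determined after the measurement and combines exposure, tolerance and time on treatment.

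The direction of the error depends on the unknown truth. A real dose effect at Cycle 3 Day 1 is understated, while a prognostic biomarker can produce an apparent dose effect, mainly at Cycle 1 Day 8 in up to 10 expansion patients. The sizes given rest on the assumed escalation chances, PFS rates and prognostic link. They indicate scale and do not predict this trial's result.

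**What to change.** In Appendix F, A.5, replace the correlation with maximum dose as follows:

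- For the Cycle 3 Day 1 change, use axitinib dose received up to that sample: the current dose and the mean daily dose from the dosing diary.
- Make no escalation-dose correlation at Cycle 1 Day 8, when no escalation has been possible.
- Report maximum dose descriptively only.
- Do not use the end-of-treatment plasma sample for the dose correlation.

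In Section 3.3, state that the Cycle 1 Day 8 ratio (axitinib alone, ASPS expansion) and the Cycle 3 Day 1 ratio (combination) are analysed separately.

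The cost is a few sentences. Section 8.5.1 already has date, time and dose recorded in the diary, and no treatment rule changes. The downside is a narrow dose range at Cycle 3 Day 1, with a ceiling of 6 mg and a mean of at most 5.46 mg twice daily, so precision will be low. That is the dose information actually available at that sample.
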